#### **4.2.7 Body Surface Area (BSA)**

The overall BSA affected by AD will be evaluated (from 0 to 100%) at each visit. One patient's palm represents 1% of his/her total BSA. BSA will be evaluated at every clinic visit.

#### **4.2.8 Dermatology Life Quality Index (DLQI) Questionnaire**

The effect of AD on patient quality of life will be self-assessed by the patient at every clinic visit starting from baseline, using the DLQI developed by Finlay and Khan (1994).

DLQI has a maximum value of thirty based on the patients response to ten questions scored according to the following scale:

- Very Much = 3
- A lot = 2
- A little = 1
- Not at all = 0
- Not relevant = 0
- Question unanswered = 0
- Question 7: "prevented work or studying" = 3

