**Please check you have answered EVERY question. Thank you.**

## 15.7 Appendix 7: Patient Orientated Eczema Measure

Patient ID #: \_\_\_\_\_ - \_\_\_\_\_ Patient Initials: \_\_\_\_\_

Visit Day: \_\_\_\_\_ Visit Date (dd-mmm-yyyy): \_\_\_\_\_

**Please circle one response for each of the seven questions below about your eczema. Please leave blank any questions you feel unable to answer.**

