#### 4.1.5 Missing values

If only the day is not known completely, for onset dates or start dates missing day information will be assumed as the 1st. If both day and month are missing, the 1st January will be used. For stop dates missing day information will be imputed as the last of the month, if both day and month are missing, the 31st December will be used.

However, if for AEs it is not clear whether the event started prior to or in the treatment period, the onset at day of first treatment will be assumed.

If it is not clear due to a missing or incomplete stop date of a medication whether the medication was taken at least once after the first treatment of the patient, a stop date after the day of the first patient visit will be assumed. The medication will therefore be classified as "concomitant medication". If it is not clear due to a missing or incomplete start date of a medication whether the medication was taken at least once before the first treatment of the patient, a start date before the day of the first patient visit will be assumed. The medication will therefore be classified as "previous medication" (cf. section 4.2.14).

Data from patients who prematurely terminate the trial will be used to the maximum extent possible.

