### 7.3 Efficacy - Secondary Endpoints Evaluation

All secondary efficacy analyses will be performed as described in chapter 6.2 with the FAS only.

IGA and EASI-75 responders at other time points will also be analysed using a GLMM model similar to that described in Section 6.1.

The efficacy variables and their changes from baseline will be summarized with descriptive statistics per treatment group and visit. This applies to the vIGA-ADTM, EASI, NRS scores for

pruritus, DLQI, POEM, SCORAD, AIS and PO-SCORAD. Change from baseline endpoints will be analysed using Mixed Model with Repeated Measures (MMRM) with Treatment Arm, Visit and Treatment x Visit Interaction as a factors and baseline value as a covariate, to account for missing data. For vIGA-ADTM as a 5-level ordinal variable, mixed ordinal logistic regression will be used with factors defined as above and IGA at baseline as a factor too.

If rescue medication is used, the patient will be specified as a non-responder from the time the rescue is used.

The following parameters will be analysed as described above:

- Proportion of patients achieving a vIGA-ADTM score of 0 (clear) or 1 (almost clear) and a decrease of at least 2 points in vIGA-ADTM in treated population compared to placebo population from baseline to Week 4, 8, 12, 18 and 20
- Change in proportion of patients achieving a vIGA-ADTM score of 0 (clear) or 1 (almost clear) and a decrease of at least 2 points in vIGA-ADTM in treated population compared to placebo population from Week 16 to Week 18 and 20.
- Absolute proportion of patients achieving EASI-75 ( $\geq 75\%$  improvement from baseline) in treated population compared to placebo population at Week 4, 8, 12, 18 and 20
- Change from baseline in vIGA-ADTM score in treated population compared to placebo population to Week 4, 8, 12, 16, 18 and 20
- Change from Week 16 in vIGA-ADTM score in treated population compared to placebo population to Week 18 and 20.
- Change from baseline in EASI in treated population compared to placebo population to Week 4, 8, 12, 16, 18 and 20
- Change from Week 16 in EASI in treated population compared to placebo population to Week 18 and 20.

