## 7.4 Efficacy - Exploratory Endpoints Evaluation

All Exploratory efficacy analyses will be performed as described in chapter 6.2 with the FAS only.

Change from baseline for exploratory endpoints (vIGA-ADTM, SCORAD, DLQI, POEM, AIS and PO-SCORAD) will be analysed using mixed model with repeated measures (MMRM) as described in chapter 7.3.

The following parameters will be analysed as described above:

- Absolut proportion of patients achieving a decrease of at least 2 points in vIGA-ADTM in treated population compared to placebo population from baseline to Week 4, 8, 12, 16, 18 and 20.
- Change in proportion of patients achieving a decrease of at least 2 points in vIGA-ADTM from Week 16 to Week 18 and 20.
- Change from baseline in the Dermatology Life Quality Index (DLQI) score in treated population compared to placebo population to Week 4, 8, 12, 16, 18 and 20.
- Change from Week 16 in the Dermatology Life Quality Index (DLQI) score in treated population compared to placebo population to Week 18 and 20.
- Change from baseline in the Patient Orientated Eczema Measure (POEM) score in treated population compared to placebo population to Week 4, 8, 12, 16, 18 and 20.
- Change from Week 16 in the Patient Orientated Eczema Measure (POEM) score in treated population compared to placebo population to Week 18 and 20.
- Change in sleep quality assessment (Athens Insomnia Scale) in treated population compared to placebo population from baseline to Week 4, 8, 12, 16, 18 and 20. The AIS endpoint should be recorded weekly (descriptive values), as defined in section 4.2.11 and p-values only provided for the weeks defined in the endpoint.
- Change in sleep quality assessment (Athens Insomnia Scale) in treated population compared to placebo population from Week 16 to Week 18 and 20. The AIS endpoint should be recorded weekly (descriptive values), as defined in section 4.2.11 and p-values only provided for the weeks defined in the endpoint.
- Change from baseline in the Patient-Oriented SCORAD (PO-SCORAD) score in treated population compared to placebo population to Week 4, 8, 12, 16, 18 and 20.
- Change from Week 16 in the Patient-Oriented SCORAD (PO-SCORAD) score in treated population compared to placebo population to Week 18 and 20.

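### Every unanswered DLQI item is scored 0 with no limit on blanks, so an incomplete form enters the MMRM as an observed score that is too low instead of as missing

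*SAP*

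**What the plan says.** SAP 4.2.8 defines the total in these words: "DLQI has a maximum value of thirty based on the patients response to ten questions scored according to the following scale". The list that follows gives 0 in three different situations: the patient reports no effect, the patient marks the item as not relevant, or the patient gives no answer. The third is the line "Question unanswered = 0". Protocol 9.1.5 has the same list. Neither section sets a maximum number of blanks, a minimum number of answers, or a condition under which the total is missing.

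No other section does so. SAP 4.1.5 covers partial dates, the MAR assumption, jump to reference and rescue. Its nearest general statement is "Data from patients who prematurely terminate the trial will be used to the maximum extent possible", which does not concern questionnaire items.

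The total is used in SAP 7.4 as an exploratory endpoint: "Change from baseline in the Dermatology Life Quality Index (DLQI) score in treated population compared to placebo population". This is done for every clinic visit after baseline, and the two follow-up visits are also compared with the end of treatment. SAP 7.4 points to the MMRM of SAP 7.3, which is specified with "baseline value as a covariate, to account for missing data".

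The DLQI form in protocol Appendix 6 closes with a request to the patient: "Please check you have answered EVERY question. Thank you".

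**The concern.** A blank is lost information, and the plan gives it the best possible item score. Three features of the documents make this hard to defend as a harmless default.

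- Items 3 to 10 of the form have a *Not relevant* box. A patient to whom an item does not apply can already say so, so a blank means something else.
- Item 1 asks about itchy, sore, painful or stinging skin and has no such box. Inclusion criterion 5 requires a worst itch NRS of at least 4 at screening and baseline, yet a blank item 1 at baseline is scored as no symptoms.
- For the daily scales the SAP averages only the scores that were reported (NRS in 4.2.6, AIS in 4.2.11). It does not fill gaps with the best value there.

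The MMRM can account for a missing total only if the total is left missing. Once blanks are filled with 0, the model treats the total as observed, and the SAP's own method for missing data is bypassed. At stake are the DLQI means in both arms and, if incompleteness differs between arms, the comparison between them.

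**Working it through.** **Inputs from the documents.** Ten items, each scored 0 to 3; unanswered item = 0; no cap on blanks (SAP 4.2.8, protocol 9.1.5). About 110 patients per arm (SAP 2).

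**Assumed inputs.** The documents give no DLQI mean and no rate of incomplete forms. I take true totals T of 10, 15 and 20, spread evenly over the items, and an excess of affected forms in one arm, f, of 2%, 5% or 10%.

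**The plan's own figure.** Maximum total = 10 × 3 = 30, as stated. The special value of 3 for Question 7 does not change it.

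**Error per form.** With mean item score m = T/10 and k blanks:

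- scored total = m × (10 − k)
- error = T − m × (10 − k) = k × m

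| Blanks k | T = 10: scored (error) | T = 15: scored (error) | T = 20: scored (error) |
|---|---|---|---|
| 1 | 9.0 (1.0) | 13.5 (1.5) | 18.0 (2.0) |
| 2 | 8.0 (2.0) | 12.0 (3.0) | 16.0 (4.0) |
| 3 | 7.0 (3.0) | 10.5 (4.5) | 14.0 (6.0) |
| 5 | 5.0 (5.0) | 7.5 (7.5) | 10.0 (10.0) |
| 10 | 0 (10.0) | 0 (15.0) | 0 (20.0) |

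The even spread is a simplification. Since each item lies between 0 and 3, the error for k blanks lies between 0 and 3k whatever the spread: 0 to 6 points for two blanks. It never makes the score too high.

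**Direction.** Take a patient whose true total falls from 15 at baseline to 10 at Week 16, a change of −5.

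- Two blanks at Week 16 only: recorded 8 − 15 = −7. Improvement is overstated by 2.
- Two blanks at baseline only: recorded 10 − 12 = −2. Improvement is understated by 3.

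**Shift in an arm mean.** If a fraction f more of the forms in one arm have k blanks, that arm's mean at the visit is too low by f × k × m. With T = 15, m = 1.5:

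| Excess f | k = 2 | k = 5 | k = 10 |
|---|---|---|---|
| 2% | 0.06 | 0.15 | 0.30 |
| 5% | 0.15 | 0.38 | 0.75 |
| 10% | 0.30 | 0.75 | 1.50 |

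An excess of 5% is 0.05 × 110 = 5.5 forms in the arm. If f = 0, both arm means move by the same amount (for equal true totals), and the comparison is not shifted but becomes noisier. Blanks at baseline occur before the first dose, so any difference between arms there is a matter of chance.

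**The case against.** The strongest case against the point is that multiple blanks should be rare. The form asks the patient to check every question, items 3 to 10 offer *Not relevant*, the eCRF raises automatic queries (protocol 12.10), edit checks look for missing data before lock (protocol 13.5), and entered data pass plausibility checks (SAP 4.1.1). The rule is also explicit and applied blind to arm, and nothing in the documents suggests that completion will differ between arms. All of this stands as a limit on size. It does not answer the point, because none of these measures says how the blanks that remain are to be scored; the only text that does gives 0.

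Four stronger readings are tempting and are not supported.

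- *A blank form scores 0 by plan.* This follows only if the item rule is applied literally to all ten items. Neither document mentions a wholly blank form, and a visit with no form at all is a different case that nothing says is scored 0.
- *POEM is zero-filled too.* The POEM form says "Please leave blank any questions you feel unable to answer", but SAP 4.2.9 and protocol 9.1.6 contain no line for an unanswered question. The documents show only that POEM has no rule for blanks. That the DLQI has such a line and POEM does not gives no ground for inferring the same treatment.
- *The error always appears as improvement and counts as treatment effect.* Baseline blanks work the other way, and the comparison is affected only under unequal incompleteness.
- *COVID-19 phone visits will raise the number of blanks.* Protocol Appendix 11 sends the scales beforehand and tells the investigator to complete all listed patient-reported assessments. It covers Weeks 4, 8, 12, 18 and 20, not Week 16, so it does not touch the end-of-treatment DLQI.

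**Conclusion.** The concern holds as a minor one. Both documents state a scoring rule that gives a wrong value for incomplete DLQI forms and hides them from the model meant to handle missing data. For one form with two blanks the error is about 2 to 4 points on the 30-point scale, under assumed true totals of 10 to 20 and an even spread over items. For the arm comparison it is much smaller and conditional: about 0.15 points (two blanks) to 0.75 points (blank forms, on the literal reading) if 5% more forms are affected in one arm and the true total is 15. With equal incompleteness the arm means are distorted but the comparison is not biased. DLQI is exploratory, so the primary and secondary efficacy endpoints, power and alpha are untouched.

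**What to change.** In SAP 4.2.8, and in protocol 9.1.5 so that the two texts still agree:

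1. Set the DLQI total to missing when more than a small prespecified number of items is unanswered. Two or more is a reasonable cut-off; it is a proposal, not a figure from the documents, and the sponsor may choose another before unblinding.
2. State that a wholly blank form is missing.

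In the SAP's outputs, add a listing of incomplete DLQI forms by arm and visit, so that a reader can see whether incompleteness differs.

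The cost is a few sentences in each document and one listing. SAP 1 and 5 already allow changes to be documented at the blind data review meeting. A few totals become missing and are handled by the MMRM under MAR, which is itself an assumption. With a cut-off of two, a single blank would still be scored 0, leaving an error of 1.0 to 2.0 points on that form under the totals assumed above.

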#### **4.2.9 Patient Orientated Eczema Measure (POEM)**

The POEM will be assessed at each clinic visit, except the screening visit. The POEM developed by Charman et.al. 2004 is a self-assessment of disease severity by the patient. POEM has a maximum value of twenty eight based on the patient's response to seven questions scored according to the following scale:

- No Days = 0

- 1-2 Days = 1
- 3-4 Days = 2
- 5-6 Days = 3
- Everyday = 4

#### **4.2.10 SCORing Atopic Dermatitis (SCORAD)**

SCORAD will be measured at each clinic visit, except the screening visit. The SCORAD grading system was developed by the European Task Force on Atopic Dermatitis (1993) and has been a standard tool to assess the AD severity in clinical studies. Six items (erythema, edema/papulation, oozing/crusts, excoriation, lichenification, and dryness) will be selected to evaluate the AD severity. The overall BSA affected by AD will be evaluated (from 0 to 100%) and included in the SCORAD scores. Loss of sleep and pruritus will be evaluated by patients on a visual analog scale (0-10). The sum of these measures represents the SCORAD which can vary from 0 to 103.

#### **4.2.11 Athens Insomnia Scale (AIS)**

The severity of sleep disturbance will be self-assessed daily starting from baseline using the Athens Insomnia Scale (AIS).

The AIS is a self-administered psychometric instrument consisting of eight items. The first five items of the AIS (assessing difficulty with sleep induction, awakenings during the night, early morning awakening, total sleep time, and overall quality of sleep) correspond to Criterion A for the diagnosis of insomnia according to ICD-10 (International Statistical Classification of Diseases and Related Health Problems 10th Revision), while the requirements of a minimum frequency (at least three times a week) and duration (1 month) of any complaint correspond to Criterion B of the ICD-10. The ICD-10 requirements of marked distress caused by the sleep problem and/or interference with ordinary activities of daily living (Criterion C) are covered through the strictly subjective nature of the response options for every item of the scale as well as through the content of the last three items pertaining to the next day consequences of insomnia (problems with sense of well-being, functioning, and sleepiness during the day).

Each item of the AIS can be rated 0-3.

The responders are requested to rate positively if they had experienced the sleep difficulty described in each item at least three times a week between the study visits (Soldatos et al. 2000).

The baseline AIS is defined as the prorated average of the AISs reported continuously for 7 days right before and on the baseline visit (i.e. study day -6 to day 1). For post-baseline AIS, the mean weekly worst itch AIS is calculated as the prorated average of the reported daily AIS within the week. For example, if there are 3 scores in a week, the prorated average = (score1 + score2 + score3)/3.

#### **4.2.12 Patient Oriented SCORAD (PO-SCORAD)**

The PO-SCORAD will be measured at each clinic visit, except the screening visit. The PO-SCORAD is the SCORAD completed by the patients themselves. It is a self-evaluation tool developed by the European Task Force on Atopic Dermatitis (2011). Six items (erythema, edema/papulation, oozing/crusts, excoriation, lichenification, and dryness) will be selected to evaluate the AD severity. The overall surface affected, loss of sleep and pruritus will also be evaluated by patients on a visual analog scale.

#### **4.2.13 Study medication: Intake and duration of intake**

The duration of intake of study medication will be calculated as day of last dispensed of study medication minus day of first dispensed of study medication plus one.

The intake of study medication will be calculated as the number of capsules dispense per visit.

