### 8.3.1 Baseline (Visit 2)

**Note: it must be ensured that inclusion criteria regarding the severity of the disease remain relatively unchanged since screening in order to exclude patients responding to the emollient use since screening visit i.e. IGA score must be unchanged and EASI score should not change by more than 10%.** Patients will attend the investigational site at Visit 2 when the following procedures/assessments will occur.

- Verification of inclusion/exclusion criteria (Sections 7.2 & 7.3)
- Patient Randomisation (as detailed in Section 10.5)
- Samples for clinical laboratory safety tests (haematology and serum biochemistry as detailed in Section 9.2.4)
- Pharmacokinetic Sampling (as detailed in Section 9.2.9)
- Biomarker Sampling (as detailed in Section 9.2.10)
- Vital signs (blood pressures, heart rate and body temperature), as detailed in Section 9.2.3);
- Physical examination (as detailed in Section 9.2.2)
- Electrocardiogram (ECG) (as detailed in Section 9.2.7)
- Dispense Study Drug
- Dispense Patient Compliance Log
- Body Surface Area (as detailed in Section 9.1.4)
- Validated Investigator's Global Assessment (as detailed in Section 9.1.1)
- Eczema Area and Severity Index (EASI) (as detailed in Section 9.1.2)
- NRS Pruritus assessment (as detailed in Section 9.1.3)
- Dermatology Life Quality Index (DLQI) Questionnaire (as detailed in Section 9.1.5)

- Patient Orientated Eczema Measure (POEM) questionnaire (as detailed in Section 9.1.6)
- SCORing AD (SCORAD) questionnaire (as detailed in Section 9.1.7)
- Athens Insomnia Scale (AIS) (as detailed in Section 9.1.8)
- Patient- Orientated SCORAD questionnaire (as detailed in Section 9.1.9)
- Concomitant medication assessment (as detailed in Section 9.2.13)
- Review emollient usage and capture
- AE assessment (as detailed in Section 11)

If all study entry criteria are satisfied the Investigator will randomize the patient and provide the patient with the DS107 capsules or placebo capsules from one of the patient treatment packs available at the site (allocated via the central randomization).

The first administration of DS107 or placebo will be carried out after the Baseline visit. Following this DS107 capsules or placebo medication will be administered once daily. IMP will be administered approximately 2 hours after food consumption at the same time each day. Patients will be instructed to not consume food for approximately 1 hour after IMP administration.

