### 8.3.5 Week 12 (Visit 6)

Patients will return to the investigational site at Week 12/Visit 6.

For accountability purposes, patients will be required to bring both the used DS107/placebo patient packs and unused DS107/placebo patient packs supplied at Visit 5. Patients will be required to provide the patient compliance log for confirmation of compliance.

The following procedures/assessments will occur:

- Vital signs (blood pressures, heart rate and body temperature), as detailed in Section 9.2.3);
- Physical examination (as detailed in Section 9.2.2)
- Dispense Study Drug
- Collect Study Drug
- Dispense Patient Compliance Log
- Collect and Review Patient Compliance Log
- IMP Accountability (as detailed in Section 10.6)
- Body Surface Area (as detailed in Section 9.1.4)
- Validated Investigator's Global Assessment (as detailed in Section 9.1.1)
- Eczema Area and Severity Index (EASI) (as detailed in Section 9.1.2)
- NRS Pruritus assessment (as detailed in Section 9.1.3)
- Dermatology Life Quality Index (DLQI) Questionnaire (as detailed in Section 9.1.5)
- Patient Orientated Eczema Measure (POEM) questionnaire (as detailed in Section 9.1.6)
- SCORing AD (SCORAD) questionnaire (detailed in Section 9.1.7)
- Athens Insomnia Scale (AIS) (as detailed in Section 9.1.8)
- Patient- Orientated SCORAD questionnaire (as detailed in Section 9.1.9)
- Concomitant medication assessment (as detailed in Section 9.2.13)
- Review emollient usage and capture
- AE assessment (as detailed in Section 11)

DS107 or placebo patient packs will be returned and additional patient treatment packs of DS107 or placebo will be supplied to the patient.

IMP will continue to be administered approximately 2 hours after food consumption at the same time each day. Patients will be reminded to not consume food for approximately 1 hour after IMP administration. The patient compliance log will be provided to the patient who will be instructed to complete this as before.

An NRS for the assessment of pruritus will continue to be captured on a daily basis from screening to the follow-up visit. Emollient use will also continue to be captured on a daily basis for the same period.

On completion of this visit, patients will be advised that they will be required to return to the investigational site at Visit 7 and to bring with them the unused DS107/placebo patient packs, the used DS107/placebo patient packs, and the patient compliance log.

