### 8.3.6 Week 16 (Visit 7) / End of Treatment or Early Termination

Patients will return to the investigational site at Visit 7. **The last dose of DS107/placebo should be taken the day before Visit 7.**

For accountability purposes, patients will be required to bring both the used DS107/Placebo patient packs and unused DS107/Placebo supplied at Visit 6. Patients will be required to provide the patient compliance log for confirmation of compliance.

The following procedures/assessments will occur:

- Samples for clinical laboratory safety tests (haematology and serum biochemistry as detailed in Section 9.2.4)
- Pharmacokinetic Sampling (as detailed in Section 9.2.9)
- Biomarker Sampling (as detailed in Section 9.2.10)
- Sample for pregnancy test (only female patients of child-bearing potential, as detailed in Section 9.2.5)
- Vital signs (blood pressures, heart rate and body temperature), as detailed in Section 9.2.3);
- Physical examination (as detailed in Section 9.2.2)
- Electrocardiogram (ECG) (as detailed in Section 9.2.7)
- Body Mass Index (as detailed in Section 9.2.8)
- Collect Study Drug
- Collect and Review Patient Compliance Log
- IMP Accountability (as detailed in Section 10.6)
- Body Surface Area (as detailed in Section 9.1.4)
- Validated Investigator's Global Assessment (as detailed in Section 9.1.1)
- Eczema Area and Severity Index (EASI) (as detailed in Section 9.1.2)
- NRS Pruritus assessment (as detailed in Section 9.1.3)
- Dermatology Life Quality Index (DLQI) Questionnaire (as detailed in Section 9.1.5)
- Patient Orientated Eczema Measure (POEM) questionnaire (as detailed in Section 9.1.6)
- SCORing AD (SCORAD) questionnaire (detailed in Section 9.1.7)
- Athens Insomnia Scale (AIS) (as detailed in Section 9.1.8)
- Patient- Orientated SCORAD questionnaire (as detailed in Section 9.1.9)
- Concomitant medication assessment (as detailed in Section 9.2.13)
- Review emollient usage and capture
- AE assessment (as detailed in Section 11)

The DS107 or placebo patient packs will be returned. No further DS107 or placebo patient packs or patient compliance logs will be issued. Following completion of the study assessments at this visit, there will be continued study restrictions in line with those described in Sections 9.2.12.

An NRS for the assessment of pruritus will continue to be captured on a daily basis from screening to the follow up visits. Emollient use will also continue to be captured on a daily basis for the same period.

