#### 10.4 Duration of Treatment

Patients will be orally administered DS107 or placebo once daily for 16 consecutive weeks.

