# 15 APPENDICES

## 15.1 Appendix 1: Study Flow-Chart

Visit	Screening/ Visit 1	Baseline / Visit 2	Week 1/Visit 3	Week 4/ Visit 4	Week 8 / Visit 5	Week 12/ Visit 6	Week 16/ Visit 7 (EOT)	Week 18/ Visit 8 (Follow up 1)	Week 20/ Visit 9 (Follow up 2)	
Day	-14 to -1	0	7	28	56	84	112	126	140	
Visit Window			+/-2 days	+/-2 days	+/-2 days	+/-2 days	+/-2 days	+/-2 days	+/-2 days	
Type of Visit	Onsite	Onsite	Telephone	Onsite	Onsite	Onsite	Onsite	Onsite	Onsite	
Informed Consent	X									
Assign Patient Identifier Number	X									
Demographics	X									
Medical/Surgical History	X									
Review Inclusion/Exclusion Criteria	X	X								
Randomization		X								
Safety Labs: Serum Biochemistry (including FSH levels at screening when applicable  ), Hematology, Virology	X	X		X	X		X	X 		
Trough Plasma Levels		X		X	X		X			
Biomarker Sampling		X					X			
Pregnancy Test (β-hCG if female of childbearing potential)	X						X			
Vital Signs	X	X		X	X	X	X	X	X	
Physical Examination 	X	X		X	X	X	X	X	X	
ECG		X					X			
BMI	X						X			
Dispense Study Drug 		X		X	X	X				
Collect Study Drug				X	X	X	X			
Dispense Patient Compliance Log		X		X	X	X				
Collect and Review Patient Compliance Log				X	X	X	X			
Discuss Patient Compliance Log			X							
IMP Accountability				X	X	X	X			
Discuss IMP Compliance			X							
BSA	X	X		X	X	X	X	X	X	
vIGA-AD TM	X	X		X	X	X	X	X	X	
EASI Assessment	X	X		X	X	X	X	X	X	
NRS Pruritus Assessment	X-----X									
DLQI Questionnaire		X		X	X	X	X	X	X	
POEM Questionnaire		X		X	X	X	X	X	X	
SCORAD Questionnaire		X		X	X	X	X	X	X	
Athens Insomnia Scale		X-----X								

PO-SCORAD Questionnaire		X		X	X	X	X	X	X
Concomitant Medications	X	X	X 	X	X	X	X	X	X
Emollient Use Capture	X-----X								
Adverse Events 		X	X 	X	X	X	X	X	X

1. FSH requirement to confirm female of non-child-bearing potential for women greater than 40 years of age who have had a cessation of menses for at least 12 months. Non-child bearing potential may also be confirmed via cessation of menses for at least 24 months without FSH levels confirmed.
2. Only if clinically significant change from baseline in safety laboratory results at Week 16.
3. Physical Examination will be symptom-directed.
4. Patients will be instructed to take their last study drug dose the day preceding Week 16 visit.
5. Collection of AEs will start after the first study drug administration.

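### SAP 4.2.13 measures duration of intake between dispensing dates, so a patient who completes 16 weeks is reported with 85 days instead of 112

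*SAP*

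**What the plan says.** SAP 4.2.13 defines two exposure variables. Duration is "calculated as day of last dispensed of study medication minus day of first dispensed of study medication plus one". For quantity, "The intake of study medication will be calculated as the number of capsules dispense per visit". SAP 7.6 (Study medication) summarises both on the Safety Analysis Set. They are reported in Table 14.3.1.1, titled as DS107 intake duration, and Table 14.3.1.2, which is described as capsules dispensed.

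The protocol fixes when drug is handed out and when it is taken:

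- The flow chart (Appendix 1) marks dispensing at Baseline, Week 4, Week 8 and Week 12, on nominal Days 0, 28, 56 and 84. At Week 12 (8.3.5), "additional patient treatment packs of DS107 or placebo will be supplied to the patient".
- At Week 16 (8.3.6), "No further DS107 or placebo patient packs or patient compliance logs will be issued".
- The COVID-19 contingency (Appendix 11) couriers drug at Weeks 4, 8 and 12 only.
- On the start of dosing, 8.3.1 says: "The first administration of DS107 or placebo will be carried out after the Baseline visit".
- On its length, 10.4 says: "Patients will be orally administered DS107 or placebo once daily for 16 consecutive weeks".
- On its end, 8.3.6 says: "The last dose of DS107/placebo should be taken the day before Visit 7". The flow chart footnote agrees: "Patients will be instructed to take their last study drug dose the day preceding Week 16 visit".

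**The concern.** The interval between the first and last dispensing is not the interval over which drug was taken. The last pack goes out at Week 12 and covers the final four weeks, and the SAP formula stops counting on the day that pack is issued. Every patient who completes treatment loses almost all of the last supply period.

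Table 14.3.1.1 is the SAP's only tabulated summary of time on drug, and its title invites the reader to take it as that. Treatment length matters in this trial. The earlier Phase 2 capsule studies lasted 8 weeks, and protocol sections 3 and 12.3 base the new study and its larger assumed effect on longer treatment. A table showing about 12 weeks of exposure where patients took 16 misdescribes what the study was set up to deliver.

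The variable also loses information. On the nominal schedule it can take only four values, so a patient who stops soon after Week 12 cannot be told apart from one who finishes.

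**Working it through.** **Inputs.** Dispensing on Days 0, 28, 56 and 84, Week 16 visit on Day 112, post-baseline windows of ±2 days (protocol Appendix 1). Last dose the day before the Week 16 visit (8.3.6). First dose after the Baseline visit, taken here as Day 0 (8.3.1). The SAP numbers study days from 1 rather than 0, but only differences enter the formulas, so the results do not change.

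**The plan's own treatment length.** 16 weeks × 7 = 112 days. From the dosing rules, last dose (112 − 1 = Day 111) − first dose (Day 0) + 1 = 112. The two agree.

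**SAP rule, nominal completer.** Last dispensing (84) − first dispensing (0) + 1 = 85. Shortfall: 112 − 85 = 27 days; 27/112 = 24.1%.

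**Visit windows.** A Week 12 visit on Days 82 to 86 gives 83 to 87 by the rule. A Week 16 visit on Days 110 to 114 gives 110 to 114 days dosed.

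- Smallest shortfall: 110 − 87 = 23 days; 23/110 = 20.9%.
- Largest shortfall: 114 − 83 = 31 days; 31/114 = 27.2%.

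**First dose on the day after Baseline.** Actual duration is 111 − 1 + 1 = 111. The rule still gives 85, so the shortfall is 26 days; 26/111 = 23.4%.

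**Early stoppers**, assuming daily dosing from Day 0 and no pack issued after the last dose. The result can only be 1, 29, 57 or 85, and the shortfall runs from 0 to 27 days:

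| Last dose (day) | Days dosed | SAP rule | Shortfall |
|---|---|---|---|
| 14 | 15 | 1 | 14 |
| 27 | 28 | 1 | 27 |
| 55 | 56 | 29 | 27 |
| 70 | 71 | 57 | 14 |
| 90 | 91 | 85 | 6 |
| 111 | 112 | 85 | 27 |

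The last two rows get the same reported value although the patients differ by 21 days of treatment.

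**Error in the other direction**, assuming a patient has stopped taking capsules but is handed one further pack. The rule then overstates by the number of days from last dose to that dispensing, 1 to 28 days. Last dose Day 20 with a pack on Day 28 gives 29 against 21 (+8); last dose Day 40 with a pack on Day 56 gives 57 against 41 (+16).

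**The case against.** The arithmetic is hard to dispute, so the case on the other side concerns weight and remedy.

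- **The consequence is small.** This stands. Adverse event tables count patients, not patient-time, and nothing in the SAP divides by exposure. Both arms are treated alike. A maximum near 87 days in a 16-week study would also look odd to an attentive reader.
- **Other output shows exposure.** Termination reasons are tabulated (14.2.3.3.1) and listed (16.2.3). Listings 16.2.9.6 to 16.2.9.8 give drug dispensed, diary compliance, and accountability with compliance. This is real mitigation, but listings do not correct the summary table.
- **The wording may be a slip for last dose.** The grammar is poor, and adding one is the usual convention for dose dates. However, the next sentence of 4.2.13, SAP 7.6 and Table 14.3.1.2 all use the word for capsules handed out, so a programmer following the SAP would use dispensing dates.
- **The overstatement case is hypothetical.** This is fair. Packs and logs are reviewed at each dispensing visit after Baseline, and patients who leave the study are called to a termination visit at which no pack is issued. It is a stated assumption, and the main result does not need it.
- **The data for the fix are not confirmed.** This stands. The documents show that doses are logged, but not that a last-dose date is a separate field.
- **The passages on early termination describe different situations and need not conflict.** This is partly fair. They still show that a visit date cannot be assumed to locate the last dose.

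**Conclusion.** The concern holds. Applied as written, SAP 4.2.13 reports 85 days for a nominal 16-week completer who was dosed for 112, a shortfall of 27 days (24.1%), or 20.9% to 27.2% across the permitted windows. This assumes daily dosing from Day 0 to the day before Week 16 and dispensing on the visit days; couriered supplies could shift the recorded dates somewhat. Patients who stop early may be understated or, if a further pack is issued after the last dose, overstated.

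The damage is limited to one descriptive exposure table. It should be corrected because following the plan exactly gives a wrong number for every completer on the protocol schedule, and the correction is cheap.

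**What to change.** 1. In SAP 4.2.13, define duration of intake as date of last dose minus date of first dose plus one, from the patient compliance log (protocol 8.3) and the IMP compliance diary data held in the IRT system (SAP 4.1.1). Update the derivation of Table 14.3.1.1. A nominal completer then gets 111 − 0 + 1 = 112.
2. If the last-dose date is missing for a patient who completed treatment, use the Week 16 visit date minus one, as 8.3.6 implies, and flag the value as imputed.
3. Set no visit-based fallback for early terminators until three protocol passages have been reconciled. Section 10.3 places the last dose on the day before the termination visit, and also labels Week 16 as Visit 6 where 8.3.6 and the flow chart say Visit 7. Section 7.5 asks for the termination visit as soon as possible after discontinuation. Section 11.4 allows a patient to be off drug but still in the study. Flag any value imputed afterwards.
4. Call the capsule count capsules dispensed, in line with SAP 7.6 and Table 14.3.1.2. A dispensed-minus-returned summary is optional, since accountability is already listed.

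The cost is SAP wording, one table derivation, an imputation flag and agreement on item 3. Before amending, confirm that a last-dose date is recorded or can be derived. The SAP already lets the blind data review meeting document changes to the planned analysis before unblinding, so a route exists.
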